9.4.3 ANALYSIS OF THE PRIMARY ENDPOINT

9.4.3.1 NDURE FEASIBILITY STUDY

For the primary endpoint (NDURE Accrual Rate), we will calculate the proportion and frequency of eligible patients who accrue (overall, white, and African American). Given its pilot nature, the study is not designed to evaluate racial differences in accrual, although reasons for study decline will be collected, analyzed for each racial subgroup, and used to refine recruitment.

9.4.3.2 RCT OF NDURE VERSUS USUAL CARE

For the primary endpoint (delays starting PORT as defined in **Section 8.4, Endpoint and Other Non-Safety Assessments**), the difference in PORT delay comparing NDURE to UC will be evaluated using a model-based approach to accommodate adjustment for randomization stratification variables. Specifically, we will use a binary regression generalized linear model (GLM) with identity link to model the probability of PORT delay as a function of treatment arm and randomization stratification variables (race and predicted location of radiation facility). We adopt this approach as opposed to a logit model or Mantel-Haenzel (MH) type approach since the estimand is the population average treatment effect, whereas the odds ratio is not collapsable and therefore inference based on logistic regression or MH estimation would be limited to a conditional treatment effect. (Additional details can be found in the FDA Guidance Document on Adjusting for Covariates in Randomized Clinical Trials.) The risk difference (PORT delay rate in UC – PORT delay rate in NDURE) will be estimated based on the treatment effect slope parameter. We will report the corresponding model-based 90% CI and two-sided p-value. We will additionally report model-based PORT delay rates for each trial arm with corresponding 90% CIs. Should GLM convergence be an issue, we will adopt an alternative approach based on subject-level predicted probabilities of PORT delay from a logistic model as outlined by Freedman⁶² and by Steingrimsson.⁶³ Analysis will be performed using the PORT delay analysis set.

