9.1.2 RCT OF NDURE VERSUS USUAL CARE

PORT Delay (Primary Endpoint)

We hypothesize that, compared with patients who receive usual care, patients who receive NDURE will have a decreased rate of PORT delay (initiation of PORT > 6 weeks after surgery). Alternatively, our null hypothesis is that there will be no difference in the rate of PORT delay between NDURE and usual care.

PORT Delay (Secondary Endpoint)

We hypothesize that, compared with usual care, NDURE will result in a smaller difference in the rate of PORT delay (initiation of PORT > 6 weeks after surgery) between AA and white patients. Alternatively, our null hypothesis is that there will be no difference in the rate of PORT delay between AA and white patients between NDURE and usual care.

TTP (Secondary Endpoint)

We hypothesize that, compared with patients who receive usual care, patients who receive NDURE will have a shorter median TTP (time, in days, between the date of definitive surgical resection to the initiation of PORT). Alternatively, our null hypothesis is that there will be no difference in median TTP between NDURE and usual care.

TTP (Secondary Endpoint)

We hypothesize that, compared with usual care, NDURE will result in a smaller difference in the median TTP between AA and white patients. Alternatively, our null hypothesis is that there will be no difference in the median TTP between AA and white patients between NDURE and usual care.

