9.2.2 RCT OF NDURE VERSUS USUAL CARE

Power and sample size calculations were performed using PASS v08.0.13, “Inequality Tests for Two Independent Proportions.” The primary endpoint for this pilot RCT is the rate of PORT delay, defined as starting PORT > 6 weeks after surgery. Our primary objective is to compare PORT delay rates between the NDURE and usual care arms. We hypothesize that, compared with patients who receive usual care, patients who receive NDURE will have a decreased rate of PORT delay (initiation of PORT > 6 weeks after surgery). Alternatively, our null hypothesis is that there will be no difference in the rate of PORT delay between NDURE and usual care. We assume the rate of PORT delay in the usual care arm will be 45%⁴⁵ and target an absolute reduction in PORT delay of 20% (rate of PORT delay in the NDURE arm = 25%)²⁴. This effect size is clinically significant and realistic given results in similar (non-randomized) interventions²⁴. Seventy-five patients in each arm yields 83% power to detect a 20% reduction in PORT delay (45% versus 25%) based on a two-sided Z-test with pooled variance of two independent proportions assuming a two-sided $\alpha = 0.1$. Our selection of $\alpha = 0.1$ and $1 - \beta = 0.8$ is based on the desire to emphasize power over type I error at this early stage of development (single-site pilot RCT) to ensure follow-up on promising interventions. Furthermore, given the trial’s design, comparison of PORT delay rates between

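### The identity-link slope used for the primary result need not equal the population-average risk difference that Section 9.4.3.2 names as its target; the fallback estimator already in that section does

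*Combined protocol and SAP*

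**What the plan says.** Section 9.4.3.2 of the combined protocol and SAP analyses PORT delay with a "binary regression generalized linear model (GLM) with identity link to model the probability of PORT delay as a function of treatment arm" plus the two stratification variables, race and predicted radiation facility. There is no interaction term. It prefers this to logistic or Mantel-Haenszel approaches because "the estimand is the population average treatment effect, whereas the odds ratio is not collapsable". The risk difference, usual care minus NDURE, "will be estimated based on the treatment effect slope parameter". If the model does not converge, the plan switches to an estimator built on "subject-level predicted probabilities of PORT delay from a logistic model".

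Section 9.1.2 states as a secondary hypothesis that "NDURE will result in a smaller difference in the rate of PORT delay" between AA and white patients. Section 9.4.4.2 tests this with a race-by-arm interaction in a similar model and the same analysis set. Section 9.4.7 plans a look at the effect by fragmentation of care between the surgical and radiation facilities.

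**The concern.** Collapsibility means that the average of the stratum risk differences, weighted by patient share, equals the marginal risk difference. It does not mean that the slope of a main-effects model uses those weights. Maximum likelihood with an identity link weights each stratum by its share divided by a binomial variance, so strata with delay rates far from 50% count for more than their share. If the risk difference is the same everywhere, the weights do not matter. If it differs, the slope and the stated estimand are different quantities, and more patients do not bring them together.

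The secondary hypothesis is a statement that the risk difference differs by race, so the primary model leaves out what the secondary objective sets out to find. Section 4.2.2 gives the effect size for a definitive trial as a reason for the design, so the number reported should be the one named as the target.

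**Working it through.** **Inputs from the documents.** 75 per arm, 45% versus 25% delay, two-sided alpha 0.10 (Section 9.2.2); 25 AA of 75 per arm and 1:1 allocation (Section 6.3); AA patients 31% more likely to be delayed, an adjusted figure (Section 2.2.2).

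**Assumptions.** 51% of patients outside MUSC. This is borrowed from the background figure for care transitions across healthcare systems in Section 2.2.5; it is not a forecast for the stratum. All facility-specific rates and effects are also assumed, because the documents give none.

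**The plan's own figure.** The pooled rate is 0.35, so the null standard error is √(2 × 0.35 × 0.65 / 75) = 0.0779. The alternative standard error is √(0.45 × 0.55/75 + 0.25 × 0.75/75) = 0.0762. Power = Φ[(0.20 − 1.645 × 0.0779) / 0.0762] = Φ(0.94) = 82.7%, which reproduces the stated 83%. The 0.0762 also gives the scale: a standard error of 7.6 points and a 90% CI half-width of 1.645 × 7.6 = 12.5 points.

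**What the slope estimates.** With one stratification factor, the large-sample slope is Σωδ / Σω. Here δ is the stratum risk difference and ω = share / (v_UC + v_NDURE), with v = m(1 − m) at the model's fitted rates m.

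**Race only, documents' figures, gap fully removed.**
- White usual-care rate: 0.45 / (2/3 + 1.31/3) = 40.8%. AA: 1.31 × 40.8 = 53.4%. Both go to 25% under NDURE.
- Effects: 15.8 points in white and 28.4 in AA patients. True average: (2/3) × 15.8 + (1/3) × 28.4 = 20.0.
- Fitted rates at the likelihood solution: white 43.1% and 23.3%, AA 48.7% and 28.9%.
- ω white = 0.667 / (0.245 + 0.179) = 1.573; ω AA = 0.333 / (0.250 + 0.205) = 0.732.
- Slope = (1.573 × 15.8 + 0.732 × 28.4) / 2.305 = 19.8. AA patients carry 31.8% of the weight instead of 33.3%.

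**Facility, effect larger outside MUSC** (MUSC 30 to 20, non-MUSC 60 to 30).
- True average: 0.49 × 10 + 0.51 × 30 = 20.2.
- Fitted rates: 35.5% and 16.6% at MUSC, 54.2% and 35.3% elsewhere.
- ω = 0.49/0.367 = 1.334 and 0.51/0.477 = 1.070. Slope = (1.334 × 10 + 1.070 × 30) / 2.404 = 18.9.

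**Facility, effect larger at MUSC** (MUSC 30 to 5, non-MUSC 60 to 45).
- True average: 0.49 × 25 + 0.51 × 15 = 19.9.
- Fitted rates: 27.2% and 5.8% at MUSC, 63.2% and 41.7% elsewhere.
- ω = 0.49/0.253 = 1.940 and 0.51/0.476 = 1.072. Slope = (1.940 × 25 + 1.072 × 15) / 3.012 = 21.4.

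**Range of patterns** (large-sample limits, one-third AA):

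| Pattern (delay %, usual care to NDURE) | True | Slope | Gap |
|---|---|---|---|
| Race only: white 40.8 to 25, AA 53.4 to 25 | 20.0 | 19.8 | −0.2 |
| Race gap removed (white 40 to 25, AA 55 to 25), facility ±10 | 20.0 | 19.65 | −0.35 |
| MUSC 30 to 20, non-MUSC 60 to 30 | 20.2 | 18.9 | −1.3 |
| MUSC 25 to 15, non-MUSC 65 to 35 | 20.2 | 18.1 | −2.1 |
| MUSC 35 to 10, non-MUSC 55 to 40 | 19.9 | 20.9 | +1.0 |
| MUSC 30 to 5, non-MUSC 60 to 45 | 19.9 | 21.4 | +1.5 |
| 20 points in every stratum | 20.0 | 20.0 | 0 |

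In a wider set of assumed rates, overstatement reached 2.2 points, in a pattern where a fitted probability sat at zero. In the race-only setting, an effect 5 to 30 points larger in AA patients gave gaps from −0.2 to +0.5. An effect 10 or 20 points larger in white patients gave +0.4 or +1.1.

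**The fallback.** Logistic regression with the same terms, with predicted risks averaged over all patients under each arm, returned the true average in every row. The logit score equations make the mean fitted risk in each arm equal the observed mean, so with randomised arms the contrast targets the average even when effects differ. Over 1,500 simulated trials of 75 per arm in each of four patterns, its standard deviation was 0.071 to 0.077, against 0.072 to 0.077 for the slope.

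**The case against.** The best defence is size. A gap of 0.2 points is about 3% of one standard error (0.2/7.6), and even 2.1 points is under 0.3 of one (2.1/7.6 = 0.28). If NDURE has no effect in any stratum the slope is centred on zero, so the test of the stated null is not biased. The trial is a pilot, race heterogeneity is examined separately in Section 9.4.4.2, and the better estimator is already named. All of this stands.

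A reader might also infer that the slope understates NDURE's benefit, by something like 0.4 to 2 points. The documents do not support that. The sign depends on where the effect is larger: the slope falls short when benefit is concentrated in high-delay strata and overshoots when it is concentrated in low-delay strata. The documents' race figures with the gap fully removed give only 0.2 points. The larger gaps need assumed facility effects. Section 9.1.2 hypothesises a narrower race gap and says nothing about facility, and Section 9.4.7 states no direction for fragmentation of care.

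The remark on Mantel-Haenszel can fairly be read as meaning its odds ratio, so that part is a matter of wording.

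**Conclusion.** The mismatch is real and small. The slope of a main-effects identity-link model is not in general the stated estimand when risk differences vary by stratum, and the plan hypothesises that they vary by race. The gap is about 0.2 points on the documents' race figures if NDURE removes the disparity. It is up to about 2 points in either direction under assumed facility rates, effects and a 51% non-MUSC share. It vanishes when NDURE has no effect in any stratum. It is also zero for a constant risk difference when race and facility effects add, and was at most 0.14 points in the non-additive cases tried.

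This is a matter of estimation, not of type I error, and it would not by itself change the trial's conclusion. It is worth correcting because the remedy is free: the plan already cites an estimator that hits the stated target, with no loss of precision in the patterns simulated.

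**What to change.** In Section 9.4.3.2, make the current fallback the primary analysis. Fit a logistic model with arm, race and predicted facility; average each patient's predicted delay risk under usual care and under NDURE over the PORT delay analysis set; report the risk difference and both arm rates with 90% CIs (delta method or bootstrap) and a two-sided p-value. Keep the identity-link model as a sensitivity analysis. This also removes a switch of primary estimator that now depends on whether the model converges.

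As a minor wording change, limit the collapsibility objection to odds-ratio estimators. It does not apply to a Mantel-Haenszel or standardised risk difference.

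The cost is a SAP text amendment. No new data, patients or methods are needed.

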9.4.4 ANALYSIS OF THE SECONDARY ENDPOINTS

9.4.4.1 NDURE FEASIBILITY STUDY

NDURE completion rate will be analyzed as 1) the percentage of enrolled patients who attend all three NDURE sessions and 2) the proportion of three NDURE sessions that are completed. For navigator caseload, we will consider the frequency of simultaneous cases navigated. Navigator time allocation for direct and indirect time, as well as patient-report measures of satisfaction with navigation will be summarized as described above for continuous data. Study questionnaire completion rate will be calculated as the proportion of pre- and post-intervention questionnaires (n=5 each) completed. Qualitative data will be analyzed using established team codebooks and focus on the content, format, delivery, and timing of NDURE. Qualitative analysis of semi-structured interviews with patients and providers following the pilot will be analyzed using established codebooks from the study team for evaluating the feasibility and acceptability of clinic-based HNSCC interventions with a focus on the content, format, delivery, and timing of NDURE.

9.4.4.2 RCT OF NDURE VERSUS USUAL CARE

PORT delay disparity (Black vs White) in NDURE vs UC: The comparison of PORT delay disparity (PORT delay in Black patients vs PORT delay in White patients) in NDURE versus UC will be evaluated using a similar GLM as described for the primary endpoint, but the model will include a race-by-treatment

arm interaction term. Model-based estimates of PORT delay disparity will be constructed for each arm with corresponding 90% CIs. The model-based difference in disparity between trial arms will be reported along with corresponding 90% CIs. Analysis will be performed using the PORT delay analysis set.

Time-to-PORT initiation, NDURE vs UC: TTP will be analyzed using cumulative incidence plots (1 – Kaplan-Meier plots) with Greenwood variance estimation to construct corresponding 90% CIs. Treatment group comparisons will be conducted using a stratified log-rank test adjusting for randomization stratification variables. As noted, TTP will be right-censored for evaluable patients who die or are lost to follow-up prior to PORT initiation, or who haven't received PORT by the end of follow-up (18 weeks post-operatively). The hazard ratio comparing the two arms will be estimated using Cox proportional hazards regression controlling for stratification variables. A sensitivity analysis will be conducted treating deaths prior to PORT initiation as a competing risk to evaluate the bias incurred in cumulative incidence estimation by right-censoring deaths. Analyses will be performed using the TTP analysis set.

Time-to-PORT initiation (Black vs White) in NDURE vs UC: TTP cumulative incidence plots (1 – Kaplan-Meier plots) will be constructed for Black and White patients randomized to NDURE and for Black and White patients randomized to UC as described. Group comparisons will be conducted using a stratified log-rank test, but controlling only for predicted radiation facility as a randomization stratification variable since a race-by-trial arm interaction term is used to evaluate this hypothesis. A Cox proportional hazards regression model will be fit as described with appropriate race-by-trial arm interaction. Censoring rules will be as described in Section 9.4.2. A sensitivity analysis will be performed treating deaths prior to PORT initiation as a competing risk. Analyses will be conducted using the TTP analysis set.

Treatment package time, NDURE vs UC: TPT is defined as the number of days between the date of definitive surgery and the date of PORT completion. Analysis will be conducted using cumulative incidence plots (1 – Kaplan-Meier plots) with Greenwood variance estimation to construct corresponding 90% CIs. Treatment group comparisons will be conducted using a stratified log-rank test adjusting for randomization stratification variables. TPT will be right-censored as described in Section 9.4.2. The hazard ratio comparing the two arms will be estimated using Cox proportional hazards regression controlling for stratification variables. A sensitivity analysis will be conducted treating deaths after PORT initiation but prior to the completion of PORT as a competing risk to evaluate the bias incurred in cumulative incidence estimation by right-censoring deaths. Analyses will be performed using the TPT analysis set.

Treatment package time (Black vs White) in NDURE vs UC: TPT cumulative incidence plots (1 – Kaplan-Meier plots) will be constructed for Black and White patients randomized to NDURE and for Black and White patients randomized to UC as described. Group comparisons will be conducted using a stratified log-rank test, but controlling only for predicted radiation facility as a randomization stratification variable since a race-by-trial arm interaction term is used to evaluate this hypothesis. A Cox proportional hazards regression model will be fit as described with appropriate race-by-trial arm interaction. Censoring rules will be as described in Section 9.4.2. A sensitivity analysis will be performed treating deaths after PORT initiation but prior to the completion of PORT as a competing risk. Analyses will be conducted using the TPT analysis set.

Time from surgery to PORT referral scheduling, NDURE vs UC: Time from surgery to PORT referral scheduling will be analyzed using the approach described for all time-to-event endpoints. Censoring rules will be as described in Section 9.4.2. Analyses will be performed using the time from surgery to PORT referral scheduling analysis set.

Time from surgery to appointment with radiation oncology, NDURE vs UC: Time from surgery to appointment with radiation oncology will be analyzed using the approach described for all time-to-event endpoints. Censoring rules will be as described in Section 9.4.2. Analyses will be performed using the time from surgery to appointment with radiation oncology analysis set.

Pre-surgical radiation consultation, NDURE vs UC: will be analyzed using a binary regression GLM with identity link as described. If the GLM fails to converge, then unadjusted (empirical) rates and corresponding 90% CIs will be constructed, with trial-arm comparisons conducted using a z-test of two independent proportions. Analyses will be performed using the FAS.

Dental evaluation prior to surgery, NDURE vs UC: will be analyzed using a binary regression GLM with identity link as described. If the GLM fails to converge, then unadjusted (empirical) rates and corresponding 90% CIs will be constructed, with trial-arm comparisons conducted using a z-test of two independent proportions. Analyses will be performed using the dental evaluation prior to surgery analysis set.

Extraction of indicated teeth, NDURE vs UC: will be analyzed using a binary regression GLM with identity link as described. If the GLM fails to converge, then unadjusted (empirical) rates and corresponding 90% CIs will be constructed, with trial-arm comparisons conducted using a z-test of two independent proportions. Analyses will be performed using the extraction of indicated teeth analysis set.

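### Time-to-PORT hypotheses are stated in median days, but the planned effect measures are all on the hazard-ratio scale, with no contrast in days and no check of proportional hazards

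*Combined protocol and SAP*

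**What the plan says.** Section 9.1.2 puts both TTP hypotheses in days. For the arms, "patients who receive NDURE will have a shorter median TTP", and "our null hypothesis is that there will be no difference in median TTP between NDURE and usual care". For disparity, "NDURE will result in a smaller difference in the median TTP between AA and white patients".

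Section 9.4.4.2 describes the analysis. For display, "TTP will be analyzed using cumulative incidence plots (1 – Kaplan-Meier plots) with Greenwood variance estimation to construct corresponding 90% CIs". For the test, "Treatment group comparisons will be conducted using a stratified log-rank test adjusting for randomization stratification variables". For the effect size, "The hazard ratio comparing the two arms will be estimated using Cox proportional hazards regression controlling for stratification variables". For disparity, curves are drawn by race within arm, and the section says that the hypothesis is evaluated through a race-by-arm interaction term in the Cox model. A sensitivity analysis treats death before PORT as a competing risk.

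Section 9.4.1 lists the median among generic summaries of continuous variables and plans checks of normality. Neither section commits to a Kaplan-Meier median for TTP, a difference in medians, a restricted mean, or a check of proportional hazards. Section 8.4.4 censors TTP at day 126 for patients alive and not yet started.

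**The concern.** The hypotheses name one quantity and the analysis estimates another. A hazard ratio does not translate into days unless the shape and spread of TTP are known, and the documents give neither. For disparity, the interaction is a ratio of hazard ratios, whereas the hypothesis concerns how far apart two medians lie in each arm. The two can disagree.

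Elsewhere the plan takes care over scale. Section 9.4.3.2 chooses a risk difference for PORT delay because it matches the estimand, and section 9.4.4.2 reports the PORT delay disparity for each arm and the difference between arms, with 90% CIs. TTP has no equivalent. If this is left as it is, the two TTP hypotheses can be answered in their own units only by choices made after the data are seen. A later trial would also inherit a hazard ratio whose meaning in days is unstated.

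**Working it through.** **Inputs from the documents.** PORT delay of 45% under usual care and 25% under NDURE at day 42, 75 patients per arm, two-sided alpha 0.10 (section 9.2.2); TTP censored at day 126 (section 8.4.4); 25 AA patients per arm (section 6.3). The documents give no TTP distribution, median or hazard ratio, and no rate at any other day.

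**The plan's own figure.** A pooled two-sided Z-test of 45% against 25% with 75 per arm gives power of 82.7%. The stated 83% is reproduced. It concerns PORT delay; no power is stated for TTP.

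**Step 1: the hazard ratio that the planning rates allow.** Write S(t) for the share not yet started at day t. Under proportional hazards, HR = ln S_NDURE(42) / ln S_UC(42) = ln 0.25 / ln 0.45 = 1.386 / 0.799 = 1.74. A value above 1 means earlier starts with NDURE.

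**Step 2: what 1.74 means in days.** For Weibull arms with common shape k that pass through both planning rates, the median is 42 × [ln 2 / (−ln S(42))]^(1/k). The bracket is 0.693/0.799 = 0.868 for usual care and 0.693/1.386 = 0.500 for NDURE.

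| Assumed shape k | UC median | NDURE median | Difference (days) |
|---|---|---|---|
| 1 | 36.5 | 21.0 | 15.5 |
| 3 | 40.1 | 33.3 | 6.7 (unrounded medians) |
| 8 | 41.3 | 38.5 | 2.7 (unrounded medians) |

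The hazard ratio is 1.74 in every row. It does not determine the quantity in the hypothesis.

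**Step 3: disparity under proportional hazards.** Assume Weibull shape 3 in all four groups, usual-care medians of 38 days (white) and 44 days (AA), and a hazard ratio of 1.74 in both races. NDURE multiplies each median by 1.74^(−1/3) = 0.83.

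- White: 38 → 31.6. AA: 44 → 36.6.
- Gap: 44 − 38 = 6.0 days under usual care; 36.6 − 31.6 = 5.0 days under NDURE.
- Interaction: 1.74 / 1.74 = 1.

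The disparity hypothesis as worded is true, and the planned model shows nothing.

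The reverse can also happen. If NDURE takes 6.4 days off both medians (to 31.6 and 37.6), the gap stays at 6.0 days. The hazard ratios are then (38/31.6)³ = 1.74 and (44/37.6)³ = 1.60, so the interaction is 1.60/1.74 = 0.92.

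**Step 4: could the hazard ratio vary over time?** The rows below are simulated shapes (3,000 trials each, 75 per arm, censored at day 126), all set to 45% and 25% at day 42. The shapes are assumptions. The last row supposes that NDURE only moves starts from days 42–56 to days 35–42.

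| Assumed shape | HR at UC 10th / 50th / 90th percentile | Average Cox HR | Proportionality test rejects at 5% |
|---|---|---|---|
| Weibull | 1.74 / 1.74 / 1.74 | 1.74 | 5% |
| Lognormal | 2.04 / 1.48 / 1.27 | 1.66 | 22% |
| Log-logistic | 2.14 / 1.42 / 1.06 | 1.59 | 30% |
| Fréchet | 2.14 / 1.22 / 1.03 | 1.63 | 70% |
| Threshold shift | 1.74 to day 42, then 0.50 over days 42–56 | 1.17 | 11% |

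The ratio may be constant, may fall towards 1 or, in the threshold case only, may reverse. With 75 per arm the test often misses such departures.

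**The case against.** A reader might infer that the plan's own target effect implies strongly non-proportional hazards. The documents do not support this. They give one pair of rates at one day, which fits a constant ratio of 1.74 exactly. Convergence of the curves by week 18 is not evidence either. If 10% of usual care has not started by day 126, proportional hazards put NDURE at 0.10^1.736 = 1.8%, so the gap narrows from 20 points at day 42 to 8.2 points with no change in the ratio. Any departure comes from a shape that the analyst assumes.

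It can also be said that medians can be read off the planned curves, that the absolute effect at the guideline threshold is already the primary estimand, that the log-rank test is valid under the null of identical TTP distributions whatever the hazard shape, and that these are secondary endpoints of a pilot. All of this stands, and it limits the weight of the point. It does not close the gap: a median read from a curve is not a planned contrast with a confidence interval, and the day-42 risk difference does not address the median hypotheses.

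Finally, restricted mean time is not the median either, and nothing in the plan makes it necessary to demote the hazard ratio. Both are fair. The restricted mean is therefore proposed only as a supplement, and the Cox model stays as planned.

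**Conclusion.** The mismatch is in the text and needs no assumption: the hypotheses are in median days, the planned contrasts are a hazard ratio and a ratio of hazard ratios, and no check of proportionality is specified. It matters most for disparity, where the interaction can equal 1 while the gap in medians shrinks, even under proportional hazards. The figures of 6.0 and 5.0 days illustrate this under assumed medians and shape; they are not forecasts. For the arm comparison, one hazard ratio of 1.74 corresponds to 2.7 to 15.5 days over Weibull shapes 8 to 1.

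Non-proportional hazards are possible but not shown, and the case for change does not depend on them. The primary analysis is unaffected. The change is worth making before analysis because it lets the trial answer two of its stated secondary hypotheses.

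**What to change.** In section 9.4.4.2, add for TTP:

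1. Kaplan-Meier median TTP by arm and by race within arm, each with a 90% CI.
2. The between-arm difference in medians, with a 90% CI (for example, by stratified bootstrap).
3. The AA-minus-white difference in medians within each arm, and the difference between arms in that gap, with 90% CIs.
4. A proportional-hazards check for the Cox models, and the difference in restricted mean TTP to day 126 as a supplementary measure.

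Items 1 to 3 should be reported whatever the check shows, since its power is low at this sample size. Keep the stratified log-rank test, the Cox hazard ratio and the interaction as planned.

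The cost is a few lines of plan text and a little programming, with no new data. On the planning rates, more than half of each arm starts by day 42, so the arm medians should be reached well before censoring. The downside is that the disparity contrast will be imprecise with about 25 AA patients per arm; the restricted mean relieves this only in part.
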